6.3.2 Primary outcome analysis

During weeks 8 and 9 of the study infants will be assessed with two forced choice tasks where they will have to extend object names to new exemplars based on visual commonalities. We will assess the statistical difference between the response pattern and chance (using t-tests). This will show whether infants have learned to extend object names by shape similarities. The factors that predict the number of noun extensions based on shape as well as vocabulary growth will be assessed using mixed effect model analyses. The most important factors tested in the models will be the number of words known before the intervention, the intervention type (shape training vs specific word training), attention measures (pre-test and attention during training), and sorting task measure. The outcome of these analyses will show whether the shape bias intervention has led to a larger vocabulary growth than the specific word intervention (as a control intervention). It will also assess the role of attention in word learning and whether only infants that pay attention to novel items

presented to them or infants that are sensitive to shape similarities between objects can acquire a shape bias. Only data of infants that complete the intervention will be analysed.

Regarding the follow up study, infants' vocabulary and cognitive abilities will be assessed. This with the aim of analysing if there are any long-term effects of each intervention and infants continue learning words and potentially "catching up", or if the intervention programmes are only beneficial while they are being implemented. The cognitive assessments will be used to assess whether the intervention has an effect on visual spatial skills and working memory. In both cases, it will be done by comparing the infants results to the standardized mean of UK infant population. Similarly, infant's result in the follow up language assessment will be compared to the standarized mean of UK infant population.

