3.1. Primary objectives

The main objectives of the present study are:

- A. To investigate whether it is possible to teach Late Talkers to attend to objects' shapes as a useful property for learning and generalizing novel object labels.
- B. To assess the benefits that this intervention programme has on Late Talkers' short-term vocabulary development compared to an intervention where infants will be taught specific words ('specific word' intervention).
- C. To assess the benefits of the intervention programme on language and cognitive development one year after the intervention compared to the 'specific word' intervention.

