3.3. Primary outcome measures

Objective A), i.e. whether children have learned a shape bias, will be assessed by means of a noun extension test with novel names and objects never heard and seen before by the infants at the end of the intervention programme.

Objective B), i.e. whether the intervention programme benefits infants' general vocabulary development, will be assessed with a vocabulary checklist filled in by the parents/guardians before and after both types of intervention. We will compare the vocabulary growth in the group of children that took part in the shape bias intervention programme with that of the group of children that took part in the 'specific word' intervention. A significant larger increase in the shape bias intervention compared to the 'specific word' intervention will provide information regarding the success or efficacy of the shape bias intervention.

Objective C), i.e. whether the shape bias intervention has a "long-term" effect on language development and cognitive abilities. Receptive and expressive language, and cognitive abilities, such as visual spatial skills and working memory, will be assessed at one year after the end of the intervention programme.

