4.3. Tests and procedure of intervention programme

4.3.1. Vocabulary and developmental assessments. At session 1, parents/guardians will fill in a socioeconomic and general development questionnaire (see Appendix 1.5). The

information provided in this questionnaire will double-check the inclusion/exclusion criteria. It will also be used to check whether the intervention was only successful in a sub-group of the infants (e.g. those without a family history of language problems). In the first and last session, parents/guardians will also be asked to fill in the UK-CDI Words and Gestures questionnaire, a vocabulary checklist of words and phrases that infants might know and use (Alcock, Meints, & Rowland, 2017; see Appendix 1.4). This will allow us to compare language development during the intervention programme between the two intervention groups.

4.3.2. Initial cognitive assessments: The initial cognitive assessments will be presented during the first two sessions. During week 1, infants will be assessed with a shape sorting task and an attention task. The sorting task will last no more than 5 minutes and will be used to assess if before the training programme, infants are sensitive to the shape of objects and can group objects by shape. Infants will be presented with 16 novel objects differing in shape, colour and texture and asked to sort them into groups. How to sort (namely by shape) will be shown to them with the means of examples. The attention task will last 3 minutes and will assess infants' joint and sustained attention. This will be achieved by monitoring their eye movements during the presentation of five short video clips (35 seconds each) of a person looking at and moving unusual novel objects. For this task, participants will sit on their parent/guardian's lap in front of a computer screen. Eye movement will be monitored with a remote eye tracker (see Figure 2). The parent will wear blacked-out glasses so that their behaviour cannot affect the infants' eye gazes.

At week 2, infants' visual spatial abilities and working memory will be assessed using the Wechsler Preschool & Primary Scale of Intelligence - Fourth UK Edition (WPPSI-IV UK). This test will last about 20 minutes and will be used to rule out any potential cognitive delay.

Figure 2. Attention task. Infants will watch five short videos and eye movements will be monitored with a remote eye tracker.

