4.3.3. Training sessions

4.3.3.1. Shape training: During the first seven weeks, infants will be presented with four novel words paired with four novel sets of objects (total duration 15 minutes). Each set will consist of two exemplars with the same shape but with different colours and textures. Each set will be presented with sentences such as “*Look! It is a kiv. Do you want to play with the kiv?, Let’s play with the kiv*”. Half way through the presentation of the exemplars, the researcher will bring out a third contrasting object. This contrasting object will be presented with the sentence “*Oh no, this is not a kiv*” and will be taken away immediately. The other three sets of novel exemplars will be presented in the same manner.

4.3.3.2. ‘Specific word’ training: This training will resemble a typical word learning intervention. During the first seven weeks infants will be introduced to 28 real common objects and their names (e.g. biscuit, trousers, slide), randomly divided into 7 sets of four words. During each session, infants will be presented with one of the sets and each session will have a total duration of 15 minutes. The target words have been selected from the Wordbank database, an open database that lists the proportion of children that know a specific word at a specific age. Twenty-eight words that 80% of the total child population at 25 months know were randomly selected as target words. Each session will consist of a 15 min play session in which each object name will be presented at least 10 times and each object name will be mentioned at least 10 times. Additionally, techniques such as focused stimulation and modelling target words, which have proved to be useful for word learning, will be used.

4.3.4. First-order generalization: At week 8 infants in both groups will be assessed as to whether they have learned that objects that have the same shape share the same name. They will be presented with each exemplar used during the training sessions accompanied by three novel toys. These three objects will share only one visual property with the training objects (colour, shape or texture). The three objects will be placed on a table and the researcher will say “*This is a kiv, Can you show me the other kiv?*” while he/she shows the infant one of the exemplars used during the 7 training weeks. All infants will be tested on each trained object with the same procedure. This test will last 8 minutes.

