4.3.5. Higher-order generalization: At week 9, all infants will be assessed with four pairs of novel objects different to the ones used in previous sessions. The same procedure as the one for the first-order generalization will be followed and it will also last 8 minutes. This test will assess if infants have learned a general rule that one can extend novel labels based on shape similarities.

At the end of the study and independent of the type of intervention that the children took part in, parents/guardians will be asked about their thoughts about the development and implementation of the study, as well as about possible changes they made at home or any activities (such as music or dancing sessions) that their infants attended to while they were part of the study (see Appendix 1.6). Additionally, they will receive a Participant Debrief Sheet with more information about the specific intervention programme that their child received (see Appendix 1.7).

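### Section 6.3.2 rests the claim that a shape bias was learned on t-tests against chance; the planned noun-extension model has an arm effect that should carry Objective A but is not given that role

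*Combined protocol and SAP*

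**What the plan says.** Objective A (Section 3.1) is "To investigate whether it is possible to teach Late Talkers to attend to" shape when learning and generalising object names. Section 3.3 sets its outcome as a "noun extension test with novel names and objects never heard and seen before by the infants at the end of the intervention programme". Section 4.3.5 describes that test: "At week 9, all infants will be assessed with four pairs of novel objects different to the ones used in previous sessions".

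Section 6.3.2 introduces the two forced-choice tests of weeks 8 and 9 and continues: "We will assess the statistical difference between the response pattern and chance (using t-tests). This will show whether infants have learned" to extend names by shape. It then plans models: "The factors that predict the number of noun extensions based on shape as well as vocabulary growth will be assessed using mixed effect model analyses". Listed as factors are words known before the intervention, intervention type, attention before and during training, and the sorting measure.

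Of the arm comparison, it says: "The outcome of these analyses will show whether the shape bias intervention has led to a larger vocabulary growth than the specific word intervention". For acquiring a shape bias, 6.3.2 and 6.3.3 spell out only the roles of attention and shape sensitivity.

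**The concern.** Whether something was taught is a causal question. A one-sample comparison with chance answers a different one: whether children choose by shape when tested. With no noun-extension measurement before training, it cannot separate a preference produced by training from one already present or one that developed over the nine weeks regardless.

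The design supplies what is needed, namely a randomised concurrent arm that takes the same week-9 test. The chance test and the arm effect can disagree, and the plan gives the learning conclusion to the chance test. At stake is reporting an untaught preference as taught, on a primary objective.

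A second, smaller problem lies in the model. Attention during training is measured after allocation and may itself depend on which training the child receives. Conditioning on it can distort the arm effect.

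**Working it through.** **1. Is there a baseline for noun extension?** The initial assessments (Sections 4.3.1 and 4.3.2) are the vocabulary checklist, background questionnaire, sorting task, attention task and WPPSI-IV. Noun extension is first tested in week 8 (4.3.4) and again in week 9 (4.3.5). The sorting task cannot stand in: "How to sort (namely by shape) will be shown to them with the means of examples", and it involves no extension of names.

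**2. Is the starting level fixed by eligibility?** No. Section 1.2 says that Late Talkers lack a shape bias, but Section 4.1.1 requires only a moderate or severe delay at 24 to 48 months, among other criteria. Section 6.3.1 itself allows a shape preference as a sorting category. The starting level is assumed, not measured.

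**3. Which week?** The t-test sentence follows the mention of weeks 8 and 9, so it reads naturally as covering both. The model's outcome week is not stated. Section 3.3 points to week 9. In week 8, "They will be presented with each exemplar used during the training sessions accompanied by three novel toys"; Section 4.3.3 gives those exemplars to the shape arm only, so they are unfamiliar to the other arm.

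**4. How often could the chance test mislead?** Assumptions not in the documents: 12 children per arm (24 completers split equally), each arm tested separately, chance 1/3 (three options), k = 4 or 8 trials per child, between-child SD s = 0 to 0.25, and the same true shape-choice rate p in both arms (no training effect).

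The child-level SD is sqrt(s² + (p(1−p) − s²)/k), and the noncentrality is (p − 1/3)·sqrt(12)/SD. The test is two-sided at 0.05, counting upper-tail rejections. Example with p = 0.50, k = 8, s = 0: SD = sqrt(0.25/8) = 0.177, noncentrality = 0.1667 × 3.464/0.177 = 3.27, rejection 0.844.

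Binomial or beta-binomial simulation gives q, the chance that the shape arm beats 1/3. The arms are independent with equal q, so shape arm above chance and control arm not has probability q(1 − q).

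| p | s | q (k = 4 / 8) | q(1 − q) (k = 4 / 8) |
|---|---|---|---|
| 0.40 | 0 | 0.130 / 0.213 | 0.113 / 0.168 |
| 0.40 | 0.15 | 0.101 / 0.129 | 0.091 / 0.112 |
| 0.40 | 0.25 | 0.075 / 0.082 | 0.069 / 0.075 |
| 0.50 | 0 | 0.564 / 0.839 | 0.246 / 0.135 |
| 0.50 | 0.15 | 0.459 / 0.631 | 0.248 / 0.233 |
| 0.50 | 0.25 | 0.335 / 0.406 | 0.223 / 0.241 |

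At p = 1/3, q is 0.015 to 0.021, so there is no inflation. A between-arm t-test on the same simulated data favours the shape arm in 0.024 to 0.026 throughout. A repeat simulation agrees with the q column to within 0.003.

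**5. Power of the arm contrast.** Section 6.1 gives 24 completers for power 0.8, a medium effect and error probability 0.05, but names no test. Taking medium as d = 0.5 and two-sided 0.05, a one-sample t-test needs 34 children and a two-sample t-test 64 per arm. A repeated-measures F test (f = 0.25) can give 24, for example with four measurements correlated 0.5, but no such settings are stated. The figure therefore cannot be attached to either noun-extension test. For the unadjusted arm contrast, the noncentrality is d·sqrt(n/2):

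- 12 per arm: 0.5 × sqrt(6) = 1.22 on 22 df, power 0.22; 80% power needs d = 1.20.
- 15 per arm: 0.5 × sqrt(7.5) = 1.37 on 28 df, power 0.26; 80% power needs d = 1.06.

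**The case against.** The strongest reply is that the right analysis is already planned. Section 6.3.2 names shape-based extensions as a model outcome and intervention type as a factor. This stands, and it narrows the point. A reader might infer that the plan compares the arms on vocabulary growth only; the text does not support that. What is missing is the statement that this contrast decides Objective A.

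Second, a reader might take 34–84% (the range of q at p = 0.50) as the risk of a false claim. That ignores the other arm. It takes the same test, and when both arms beat chance the problem is visible. In the 84% cell, that happens in about 0.839² = 70% of trials. The misleading one-arm pattern is the fairer measure. The rates 0.40 and 0.50 are also hypothetical, and under the protocol's own premise of no shape bias the risk is small.

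Third, Objective A names no comparator, unlike B and C, and the comparator is active. Specific-word training uses real objects, and Section 1.1 says that object categories tend to be organised by shape, so it might also foster shape extension. This stands too. A reader might infer that a null arm contrast shows that Late Talkers cannot be taught; neither the comparator nor the power supports that. It is a reason to keep the chance comparisons in the report, but not to let them carry the causal claim.

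**Conclusion.** The concern holds in a limited form. The plan attaches the learning conclusion to a test that cannot attribute a shape preference to training, and does not name the planned randomised contrast as the basis for Objective A. It also lists a post-allocation attention measure in the same model.

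On the stated assumptions and with no training effect, the shape arm beats chance in about 7–21% of trials at a true rate of 0.40 and 34–84% at 0.50. The shape arm alone does so in about 7–17% and 13–25%, against about 2.5% for a between-arm test. There is no inflation at 1/3. These figures illustrate the mechanism; they do not estimate the risk in this trial, because the documents give no untrained shape-choice rate. The textual point does not depend on them. The change should be made, and it concerns how the analysis is designated, not the design.

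**What to change.** In Section 6.3.2:

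1. Base the claim that training taught a shape bias on the intervention-type effect, with its confidence interval, on the week-9 novel-object test in the already planned mixed model.
2. In that model, adjust only for baseline factors: words known, pre-test attention and sorting category. Keep attention during training for the secondary analysis.
3. Report the comparisons with chance for both arms side by side, as supporting evidence that does not by itself show teaching.
4. Report week 8 as supportive, because its exemplars are familiar only to the shape arm.

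In Section 6.1, say which test the 0.8 power refers to, and disclose the power of the week-9 arm contrast.

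The cost is SAP wording; data, visits and enrolment are unchanged. The price is a low-powered contrast that measures the effect over specific-word training, not over no training. Adjustment changes this modestly. The approximation used is a child-level linear model with five baseline parameters (one for words, one for attention, three for the four sorting categories). At d = 0.5, with baseline factors explaining an assumed 0%, 30% or 50% of the variance, power is 18%, 23% or 30% with 12 per arm, and 22%, 30% or 39% with 15. The interval should therefore lead the report, and a null result should be described as inconclusive about whether a shape bias can be taught.

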6.3.1 Summary of baseline data

From the total number of assessments and tasks, results from five of them will be used as baseline data or descriptive statistics. These five assessments are: Vocabulary checklist, Socioeconomic and general development questionnaire, attention task, sorting task, initial working memory assessment, and initial visual spatial abilities assessment. The description of the variables analysed on each assessment and how they will be reported is as follows.

- A. Vocabulary assessment: Parents will fill out this checklist before (and after) the intervention and the total number of words that the infant understands and the total number of words they

produce will be registered as continuous variables and will be considered as the baseline language ability before the intervention programme.

- B. Socioeconomic and general development questionnaire: This questionnaire will provide information regarding general child development, language delay family history, and family status. A number of different types of variables will be collected: nominal variables (e.g. occupation) and ordinal variables (e.g. infant's order of birth). These variables will be used for descriptive statistics. They are potentially interesting as predictor variables, but the sample size is likely too small to draw any strong conclusions.
- C. Attention measure: With this measure, we will assess the fixation duration (number of milliseconds an infant looks) towards a novel object that is moved. The object will be moved for 25 seconds (25000 ms) and the infant's total looking time towards the screen will be registered. This variable will be registered as a continuous variable and used as a predictor of the primary outcome measures.
- D. Sorting task: This will be registered as a categorical variable. Infants will sort objects and depending on their sorting tendency they will be assigned to one of four categories: preference for shape, preference for colour, preference for texture, no preference. This variable will be used as a predictor of the primary outcome measures.

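### Starting vocabulary is tested as a predictor of vocabulary growth, but if growth is last minus first checklist total, reporting error biases that slope downward and a test against zero is invalid

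*Combined protocol and SAP*

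**What the plan says.** Section 6.3.2 names two outcomes and one type of model: "The factors that predict the number of noun extensions based on shape as well as vocabulary growth will be assessed using mixed effect model analyses". Its next sentence begins "The most important factors tested in the models will be the number of words known before the intervention" and goes on to intervention type, the attention measures and the sorting measure. Baseline words thus stand in a list of tested factors. They are not described as an adjustment covariate.

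Vocabulary "will be assessed with a vocabulary checklist filled in by the parents/guardians before and after both types of intervention" (section 3.3). Section 4.3.1 fixes the timing: "In the first and last session, parents/guardians will also be asked to fill in the UK-CDI Words and Gestures questionnaire". Section 3.3 describes the comparison as one of growth, "We will compare the vocabulary growth in the group of children", and the success criterion as "A significant larger increase in the shape bias intervention" than in the other arm.

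Section 6.3.1, item A, records two first-session totals, words understood and words produced, which "will be considered as the baseline language ability before the intervention programme". The plan does not say which of them is meant by words known, or which defines growth. It gives no formula for growth and no reliability for the checklist. It does not mention measurement error or regression to the mean.

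**The concern.** If growth is the last total minus the first, the first total is both a predictor and, with a minus sign, part of the outcome. A parent who under-reports at session 1 makes the child look both low at the start and fast-growing. One who over-reports does the reverse. This produces a negative association even when true growth has nothing to do with true starting vocabulary.

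At stake is one tested coefficient. A significant negative slope would naturally be read as showing that Late Talkers with the fewest words gain most. That reading is tempting here because section 3.2 asks whether some children are more receptive to the programme than others. The same bias can hide or reverse a real tendency for children with more words to gain more.

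**Working it through.** The plan gives no figure for this slope, so there is none to reproduce.

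**Inputs from the documents.** Two checklist administrations (sections 3.3 and 4.3.1); two randomised groups (4.2); error probability 0.05 (6.1); a minimum of 24 completers and a recruitment target of at least 30 (6.1).

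**Assumptions not in the documents.** Growth is last minus first on the same count; 1:1 allocation; two-sided test; independent errors of equal variance at the two sessions; checklist reliability R of 0.9, 0.8 or 0.7; true-growth SD g of 0.3 to 0.8, in units of the observed baseline SD. The model is growth on arm and baseline total only.

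**Expected slope.** Write first = T + e1 and last = T + G + e2, where T is true starting vocabulary and G true growth. Let b be the true slope of G on T. With observed baseline variance 1, var(T) = R and var(e1) = 1 - R. Then

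cov(last - first, first) = bR - (1 - R), so the expected slope is R(1 + b) - 1.

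With no true relation (b = 0) this is -(1 - R): -0.10, -0.20 and -0.30 at R = 0.9, 0.8 and 0.7. The bias relative to b is -(1 - R)(1 + b).

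**False-positive rate of the test against zero, b = 0.** For b = 0 the residual variance is g² + 2(1 - R) - (1 - R)². Example: R = 0.8, g = 0.3 gives 0.09 + 0.40 - 0.04 = 0.45. With 24 children in two arms the standard error is about √(0.45/22) = 0.14, so the estimate is centred about 0.20/0.14 = 1.4 standard errors below zero. Simulation of 20,000 trials per setting gives:

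| Reliability | Expected slope | 24 completers, g = 0.3 to 0.8 | 30 completers, g = 0.3 to 0.8 |
|---|---|---|---|
| 0.9 | -0.10 | 14% to 8% | 16% to 9% |
| 0.8 | -0.20 | 27% to 14% | 33% to 18% |
| 0.7 | -0.30 | about 41% to 24% | about 49% to 30% |

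Repeat runs differ by about one percentage point. Nearly all rejections are in the negative direction, where the nominal rate is 2.5%. With error-free checklists (R = 1) the negative rejection rate returns to about 2.5%. At R = 0.95, with true-growth SD from 0.2 to 1.0 of the true baseline SD, it is 9% to 4% with 24 completers.

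**When a true positive relation exists.** The expected slope turns positive once b > (1 - R)/R. For b = 0.2 and R = 0.9 it is 0.9 × 1.2 - 1 = +0.08. For b = 0.3 and R = 0.8 it is 0.8 × 1.3 - 1 = +0.04. For b = 0.3 and R = 0.7 it is 0.7 × 1.3 - 1 = -0.09, so a real positive relation appears negative.

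**The intervention estimate.** If last - first = a + c·arm + s·first, then last = a + c·arm + (s + 1)·first. The arm coefficient c is the same in both forms (differences of about 1e-15 in simulation), and the type I error of the arm test stayed at 4.5% to 5.4%. Using the last total as outcome only adds 1 to the baseline slope; it does not remove the error bias from it.

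**Arm-by-baseline interaction.** If the true slopes in the two arms are b1 and b0, the difference in expected slopes is R(b1 - b0). This is zero when the true slopes are equal, because first-session error is common to both arms. Simulated false-positive rates were about 5% in every setting.

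**The case against.** The strongest reply is that nothing the trial sets out to conclude depends on this slope. Section 6.3.2 says the models will address the intervention effect, attention and shape sensitivity; 6.3.3 repeats only attention and sorting; and none of objectives A to E concerns starting vocabulary. Adjusting a randomised comparison for baseline vocabulary is good practice, and the arm estimate is the same whichever outcome form is used. This stands, and it is why the point is minor. It does not remove the point, because the plan says the factor will be tested and sets no limit on how the result is read.

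A second reply is that the shared term is inferred. Growth has no formula, the understood and produced totals are not distinguished, and a mixed model could be fitted to both sessions' totals instead of a difference. This also stands in part. If different counts were used for predictor and growth, the coupling would act only through correlated errors. Last minus first remains the natural reading of a before-and-after checklist and a larger increase, and the ambiguity is itself a reason to define the terms.

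Third, the size rests on assumed reliability and growth SD, and the simulated model leaves out the attention and sorting factors. That is so. At reliability 0.9 the inflation is modest, at 8-14% with 24 completers.

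A reader might infer that error forces a negative slope. It does not: with b = 0 the fitted slope was negative in 59% to 97% of simulated trials with 24 completers, depending on the setting, and a large enough true positive relation gives a positive expected slope. A reader might also infer that the trial plans to report that children with fewer words gain more. The documents state no such hypothesis or conclusion.

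**Conclusion.** The point holds, as a minor one. If growth is the last minus the first total of the same checklist count, the planned test of starting vocabulary as a predictor of growth has the wrong null. Under the assumptions listed in the working, it rejects falsely in about 8-41% of trials with 24 completers and 9-49% with 30, against a nominal 5%. The range is wide because the documents give neither a checklist reliability nor a growth SD.

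The harm is confined to this one coefficient in the growth model. A stronger reading, that the comparison of shape training with specific word training is compromised, is not supported: that estimate and its error rate are unaffected. The noun-extension model shares no term with the baseline checklist, so the concern does not reach it.

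**What to change.** In section 6.3.2:

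- Define growth, and say whether the understood or the produced total is used, for growth and for the baseline factor.
- Keep baseline words in the growth model as an adjustment covariate. State that the slope will not be tested or interpreted as a predictor of growth. This statement is the operative change; switching the outcome to the last total is acceptable but does not repair the slope.
- If differential benefit by starting vocabulary is of interest, test the arm-by-baseline-words interaction and label it exploratory at this sample size.
- Keep baseline words as a predictor of noun extensions.

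Relating growth to the mean of the two totals should not be used as a substitute. When true growth is independent of starting level, its covariance with that mean is half the growth variance, which is positive. In simulation at growth SD 0.8 that test rejected falsely in 26-44% of trials.

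The cost is a few sentences in 6.3.2, with no change to data collection or to the intervention comparison. What is given up is a simple claim that starting vocabulary predicts growth.
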